5.4. Secondary Endpoint(s) Analysis

5.4.1. Key Confirmatory Secondary Endpoint(s)

The key secondary endpoints include the following at Week 16 and Week 32:

- Change from baseline in CFR at Week 16
- Change from baseline in absolute GLS at Week 16 and Week 32.
- Change from baseline in carotid-femoral pulse wave velocity (cfPWV) at Week 16.
- Change from baseline in cfPWV at Week 32.
- Change from baseline in CFR at Week 16 and Week 32 among participants with CFR in the ranges of 2 to >2.75 and ≤ 2.75 to 3.5 at baseline.
- Change from baseline in CFR at Week 16 and Week 32 among nicotine users and non-users.
- Change from baseline in absolute GLS at Week 16 and Week 32 among nicotine users and non-users.
- Change from baseline in cfPWV at Week 16 and Week 32 in nicotine users and nonusers.
- Rate of Adverse Events (AEs) among participants treated with guselkumab at Week 16 and Week 32.

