#### 9. STATISTICAL CONSIDERATIONS

Statistical analysis will be done by the Sponsor or under the authority of the Sponsor. A general description of the statistical methods to be used to analyze the efficacy and safety data is outlined below. Specific details will be provided in the Statistical Analysis Plan.

Descriptive statistics, such as mean, standard deviation (SD), median, inter quartile range, minimum, and maximum for continuous variables, and counts and percentages for discrete variables will be used to summarize most data. In addition, graphical data displays (eg, line plots) and participant listings may also be used to summarize/present the data.

In general, for continuous or ordinal efficacy endpoints, a Mixed-Effect Model Repeated Measures (MMRM) model will be used. Covariates such as BMI, smoking status, presence, or absence of PsA, age, gender, left ventricular mass index and hypertension diagnosis will be incorporated into these models. For binary efficacy endpoints, 95% confidence intervals for binomial proportions will be provided using exact methods, such as Clopper-Pearson or Chan-Zhang.

In general, all statistical tests will be performed at a 2-sided significance level of  $\alpha$  0.05.

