## 9.4. Statistical Analyses

This section of the protocol is a summary of the planned statistical analyses of the most important endpoints including primary and key secondary endpoints. The Statistical Analysis Plan will be finalized within 3 months of "first patient in" (FPI). It will include a more technical and detailed description of the planned statistical analyses.

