1. INTRODUCTION

This statistical analysis plan (SAP) contains the definitions of analysis sets, key derived variables, and statistical methods to evaluate the safety and efficacy of guselkumab in adult participants with moderate to severe plaque psoriasis Protocol CNTO1959PSO4015. Analysis results titles, mockups, and programming instructions for all statistical outputs (tables, figures, and listings) will be provided in a separate document entitled Data Presentation Specifications (DPS).

This current SAP covers the analyses to be performed following the Sponsor decision to prematurely terminate the study on 31 MAY 2023 due to slow enrollment.

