3. SAMPLE SIZE DETERMINATION

The initial sample size calculation was based on the assumption that participants will show an average increase of 20% in CFR at Week 32. To detect a CFR, mean change of 0.3 from baseline with 80% power, and assuming a standard deviation of 0.8 and a 5% dropout rate, 50 participants are expected to be enrolled in the study. Sample size may be increased if the dropout rate is higher than expected, in accordance with the sample size assumptions stated above.

After the decision to prematurely terminate the study, this sample size calculation was no longer relevant.

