5. STATISTICAL ANALYSES

5.1. General Considerations

Descriptive statistics (eg, mean, median, standard deviation (SD), minimum, and maximum) will be used to summarize continuous variables. Counts and percentages will be used to summarize categorical variables. Graphic data displays may also be used to summarize the data. In addition, graphical data displays (eg, line plots) and participant listings may also be used to summarize the data.

The summarized data will be presented by Nicotine-user, non-Nicotine user and total group.

Baseline Value: For all endpoints the last non-missing measurement prior to or on the day of the first administration of the study treatment (guselkumab) will be the Baseline value in the study (i.e., at 'Week 0, Baseline' analysis visit, following assignment of the actual visits using visit windows, as indicated in Table 2).

Level of Significance: In general, all tests will be performed at a 2-sided significance level of 0.05, unless otherwise specified. All interval estimations will be reported using 2-sided 95%CI. Nominal p-values will be presented.

Change from Baseline:

For the continuous variables pertaining to the cardiology outcomes, skin related outcomes, or paper PRO outcomes the determination of change from baseline will be determined only when both, baseline and the measurement for the particular visit is available.

Change from Baseline at visit x = Measurement from the visit x - Baseline value of the parmeter

The number of patients with missing change from baseline values will be also presented in the statistical outputs.

For continuous or ordinal efficacy endpoints, a Mixed-effect Model for Repeated Measures (MMRM) will be used. Covariates such as Nicotine use, body mass index (BMI), presence, or absence of PsA, age, gender, and visit will be incorporated into these models.

For binary efficacy endpoints, 95% confidence interval [CI] for binomial proportions will be provided using exact methods, such as Clopper-Pearson or Chan-Zhang.

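### SAP 5.4.1 labels its secondary endpoints confirmatory, but the plan offers only nominal p-values and no multiplicity control

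*SAP*

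**What the plan says.** **Status of the endpoints.** SAP 5.4.1 carries the heading "Key Confirmatory Secondary Endpoint(s"; the sentence beneath it speaks only of key secondary endpoints. The list starts with "Change from baseline in CFR at Week 16" and "Change from baseline in absolute GLS at Week 16 and Week 32", continues with cfPWV at both visits, CFR by baseline CFR category, and all three markers by nicotine use, and ends with adverse event rates. Protocol section 3 calls the same endpoints secondary. Protocol 9.4 mentions key secondary endpoints. The protocol does not use the word confirmatory for them.

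**Error control.** SAP 5.1 sets a two-sided 0.05 level for tests in general, asks for 95% CIs, and adds "Nominal p-values will be presented". Neither document orders the tests, divides alpha or adjusts p-values.

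**Timing.** Protocol 9.4 says "The Statistical Analysis Plan will be finalized within 3 months of" first patient in. SAP version 1.0, the initial release, was approved on 21 July 2023 and covers analyses "following the Sponsor decision to prematurely terminate the study on 31 MAY 2023 due to slow enrollment".

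**Covariates.** Protocol section 9 gives examples of model covariates, ending with "left ventricular mass index and hypertension diagnosis will be incorporated into these models". SAP 5.1, 5.3.3.1 and 5.4.1.3 contain neither of these two. SAP Appendix 2, which lists departures from the protocol's analyses, mentions neither the covariates nor the date of the SAP. It does disclose the change from three baseline CFR categories to two.

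**Sample size.** SAP section 3 states: "After the decision to prematurely terminate the study, this sample size calculation was no longer relevant".

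**The concern.** To call an endpoint confirmatory is to say that a significant result supports a claim at a known error rate. That needs a defined family of tests and a rule holding the family's false-positive rate at the stated level. Here the p-values are nominal by the SAP's own account, so the heading in 5.4.1 and the statement in 5.1 contradict each other.

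At stake is how a single low p-value would be reported. With many results and no ordering, one nominal p<0.05 is quite likely by chance, and under this heading it could be presented as a confirmed finding. The word also enters in a SAP first approved after the study was stopped, and the protocol had not used it. A reader should therefore be told what was known when the document was approved.

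**Working it through.** **Plan's own figure.** Neither document states a familywise error rate or a number of tests, so there is nothing to reproduce.

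**Inputs.** The list in SAP 5.4.1; two-sided 0.05 per test from SAP 5.1; the comparison of nicotine users with non-users in SAP 5.3.3.1 and 5.4.1.3.

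**Step 1, count the efficacy results.**

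| Row | If each subgroup's change is tested | If subgroups are compared |
|---|---|---|
| CFR overall, Week 16 | 1 | 1 |
| GLS overall, 2 visits | 2 | 2 |
| cfPWV overall, 2 visits | 2 | 2 |
| CFR by 2 baseline categories, 2 visits | 2 × 2 = 4 | 2 (differences) or 4 (within category) |
| 3 markers by nicotine use, 2 visits | 3 × 2 × 2 = 12 | 3 × 2 = 6 |
| Total | 21 | 13 or 15 |

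The two adverse event rates in the same list are left out, because no test is described for them.

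**Step 2, chance of at least one p<0.05 with no effect anywhere, independent tests.** The formula is 1 − 0.95^k.

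- k = 5 (overall results only): 1 − 0.95^5 = 22.6%
- k = 13: 1 − 0.95^13 = 48.7%
- k = 15: 1 − 0.95^15 = 53.7%
- k = 21: 1 − 0.95^21 = 65.9%

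**Step 3, allow for correlation.** Subgroup results overlap with the overall results, and visits and markers are correlated, so independence overstates the risk. A simulation of the 21 one-sample t-tests (20,000 runs per row) used nicotine groups of 20 and 30 for N = 50, or 8 and 12 for N = 20, with equal CFR categories. The correlations and N are assumptions; the documents give no correlations and no final N.

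| Visit correlation | Marker correlation | N = 50 | N = 20 |
|---|---|---|---|
| 0.5 | 0.0 | 55.0% | 56.3% |
| 0.5 | 0.3 | 53.2% | 54.3% |
| 0.8 | 0.3 | 47.6% | 49.2% |
| 0.8 | 0.6 | 43.2% | 44.9% |

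For scale, a Bonferroni level for 21 tests would be 0.05/21 = 0.0024.

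**Step 4, timing.** From 31 May to 21 July 2023 is 51 days. The date of first patient in is not given, so the delay against the protocol's three-month target cannot be computed.

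**Step 5, reading the primary.** Take the planned SD of 0.8, an assumed N of 20 and a simple one-sample interval. The 95% half-width is t(0.975, 19) × 0.8/√20 = 0.37. An estimate of 0.10 gives −0.27 to 0.47, which contains both 0 and the planned 0.3. An estimate of −0.10 gives −0.47 to 0.27, which contains 0 but excludes 0.3. Containing zero is therefore not enough to call a result inconclusive; containing both values is.

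**The case against.** The label is one heading. The text below it says key secondary, and SAP 5.1 already calls the p-values nominal and asks for 95% CIs, so much of the remedy is in place. That is fair, and it makes the fix small. It does not remove the contradiction between the heading and 5.1.

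The count of tests can be disputed. SAP 5.3.3.1 and 5.4.1.3 describe a comparison of nicotine groups, and no CFR-category term appears in the models, so p-values for the category rows are an assumption. This stands, and it is why a range is given. If the category rows carried no p-values, the count would be 5 + 6 = 11 and the chance 1 − 0.95^11 = 43%, still far above 5%. Adding the primary to reach 22 independent tests (68%) is not justified: the primary is not part of the secondary family, and the results are correlated.

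A reader might infer that the analysis was shaped by the results. The documents do not show this. They do not say that anyone writing the SAP had seen outcome data. CFR and GLS go to a core lab for blinded review, and the SAP describes data cleaning and database lock as still ahead. The recut of the CFR categories is disclosed in Appendix 2, with low numbers as the reason.

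A reader might also infer that the SAP breached a fixed protocol model. Protocol section 9 introduces its covariates as examples and leaves details to the SAP. An entry in the change log would be good practice, but leaving out two examples does not by itself make an endpoint non-confirmatory.

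**Conclusion.** The confirmatory label in SAP 5.4.1 is wrong as written. The secondary family has no error control. With no effect, the chance of at least one nominal p<0.05 is about 49% to 66% for 13 to 21 independent tests, and about 43% to 56% for 21 tests under the assumed correlations. These figures rest on how the subgroup rows are tested and on assumed N and correlations, but every reading is far above 5%.

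It would be tempting to conclude that nothing in the SAP can be confirmatory. The documents do not support that. The protocol had already fixed the primary endpoint, the MMRM approach and the two-sided 0.05 level, and multiplicity among the secondaries does not touch a single primary. The primary's limits are different: a single-arm design and a sample-size basis that the SAP itself sets aside. Nor does it follow that any primary interval containing zero is inconclusive, as the worked example shows.

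**What to change.** - Retitle 5.4.1 *Secondary endpoints (descriptive)*. State that its p-values are descriptive, that no significance claim is made beyond the protocol-specified primary, and that results are reported as estimates with 95% CIs.
- In Appendix 2, record that left ventricular mass index and hypertension diagnosis, named as example covariates in Protocol section 9, are not in the SAP models.
- In Appendix 2, also record that SAP version 1.0 was approved on 21 July 2023, after termination on 31 May 2023, and state what outcome data, if any, had been accessed by then.
- For the primary, state that a 95% CI containing both 0 and 0.3 is inconclusive.
- Optionally, list CFR change by the protocol's three baseline categories. Run a sensitivity model with the protocol's covariates only if those data were collected and the sample supports it. With few participants, two more terms could overfit the model or stop it converging.

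The cost is SAP wording, plus at most one listing and one model run. The downside is that the sponsor gives up the word confirmatory for these endpoints.

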Key efficacy evaluations will be carried out at the time-points detailed in the Schedule of Activities, and will include cardiology assessments (cfPWV, GLS and CFR), and skin assessments (IGA, PASI and BSA). Efficacy assessments will be done locally at the sites. The CFR assessments for eligibility will be immediately evaluated on-site at Screening Visit S2 and Week 0. All the CFR and GLS assessments in the study will be reviewed by a cardiology core lab for blinded analysis of endpoints. Quality-of-life and lifestyle changes during the study will be measured using the Dermatology Life Quality Index (DLQI), Pittsburg Sleep Quality Index (PSQI) and Alcohol Use Disorders Identification Test (AUDIT) questionnaires, and mood and anxiety will be assessed using the Hospital Anxiety and Depression Scale (HADS, if available).

Safety evaluations will include monitoring of vital signs, 12-lead electrocardiogram (ECG) at Screening Visit S1, monitoring of tuberculosis status, pregnancy testing at each visit, and recording of AEs throughout the study. Biomarker assessments will include the evaluation of relevant markers in serum, plasma, and urine for all participants.

For participants completing the study, the total duration will be 40 weeks, including 28 weeks of treatment and a Final Efficacy Visit 4 weeks later (Week 32). The Final Safety Visit will occur 12 weeks after the last dose of the guselkumab (Week 40). Participants who discontinue guselkumab prior to Week 28 will be considered to have completed the study if they complete all the assessments of the Final Efficacy Visit at the time of discontinuation (or soon after), and the Final Safety Visit scheduled 12 weeks after the last guselkumab dose. For participants who opt to receive commercially available guselkumab from their healthcare provider after Week 28, the visit at which the first dose of guselkumab is received outside the study (Week 36) will be considered as the Final Safety Visit.

An interim analysis will be conducted after a sufficient proportion of the participants (to be defined during the study) have accrued Week 16 CFR measurements. The scope of the interim analysis will be developed and documented in a statistical analysis plan.

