## 8.1. Efficacy Assessments

Every effort should be made to ensure that the cardiology physician or designee who performed the cardiology efficacy assessments (cfPWV, GLS and CFR) for a participant at Week 0 should also perform the evaluations for the participant at Week 16 and Week 32. Every effort must be made to perform the assessments at the same lab, on the same machine, using the same software for all the visits. Assessments should be processed per the guidelines from the core lab. All CFR and GLS assessments must be recorded. The results from GLS and CFR assessments will be securely transmitted to the cardiology core lab for blinded independent review of endpoints, per guidelines laid down in the process document of the core lab. To determine eligibility, the CFR results obtained at the study site will be used. The use of contrast media for assessments is not permitted. Sites staff will be trained by the Sponsor or designee to perform the CV assessments to ensure standardization of the procedures.

The following assessments will be carried out as detailed in the Schedule of Activities. The efficacy assessments will be performed locally at the sites.

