5.3.1. Definition of Endpoint

5.3.1.1. Coronary flow reserve (CFR)

Coronary flow reserve will be measured non-invasively using transthoracic doppler echocardiography, using a high-resolution ultrasound system with a suitable transducer and the respective software. The acoustic window will be around the midclavicular line in the fourth and fifth intercostal spaces in the left lateral decubitus position. Long-axis views of the left ventricle will be obtained, and the ultrasound beam will then be angled laterally and superiorly to image the anterior interventricular groove. The coronary blood flow in the distal portion of the left anterior descending artery (LAD) will be examined with the help of color Doppler flow mapping. A sample volume will be positioned on the color signal in the LAD, and Doppler spectral tracings of flow velocity will be recorded. First, the baseline spectral Doppler signals in the distal portion of the LAD will be recorded. Then 140 µg/kg/min adenosine, a coronary vasodilator, will be administered for 5 minutes. Doppler signals will be recorded continuously at baseline and during the period of adenosine infusion. Measurements of hyperemic coronary flow velocity will be done continuously during the adenosine infusion, and the CFR measurement will be recorded based on the guidelines provided by the cardiology core lab.

Cardiac parameters, along with strain and coronary parameters will be assessed by the cardiology core lab as defined in the process document of the core lab.

The primary endpoint for the study is the change from baseline in CFR at Final Efficacy Visit (Week 32) based on FAS.

Data Handling of Primary Efficacy Endpoint

For most of the secondary efficacy analyses (eg, over time summaries), after the treatment failures are applied, no imputation will be performed for missing data (eg, lost to follow-up, missed study visit) and the values will remain as missing and as observed data will be used for the analysis.

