5.4.1.2 Estimand

Secondary Trial Objective: To evaluate the effect of guselkumab on CFR/GLS/cf-PWV measured by transthoracic doppler-echocardiography, in participants with moderate-to-severe psoriasis and intermediate cardiovascular risk. Intermediate cardiovascular risk is defined by CFR ≥ 2 and ≤ 3.5 at Screening Visit S2.

Estimand Scientific Question of Interest: What level of change from baseline of CFR/GLS/cf-PWV considered to have benefited from guselkumab for the pre-specified duration (16 weeks).

Study intervention:

• Guselkumab (100 mg SC [Subcutaneous] injections at Week 0, 4, 12, 20 and 28)

Population: Participants with moderate to severe plaque psoriasis (with or without PsA) for at least 6 months prior to study entry. The target population consists of men or women aged 18 years and above with moderate to severe plaque psoriasis of at least 6 months' duration, defined as PASI \geq 12, and involved BSA \geq 10% at Screening Visit S1 and CFR with \geq 2 to \leq 3.5 at Screening Visit S2. Participants should not be with CFR of \leq 0 r \geq 3.5 at both Screening Visit S2 and Week 0.

Variable: Change from baseline in the CFR measurement at Week 16. The CFR measurement at Week 0, Baseline will be considered as baseline value. Similarly, for other secondary endpoints of GLS/cf-PWV at Week 16 and Week 32. Participants who had adequate secondary endpoint measurements will be assessed at Week 16 as per Table 2 and Final Efficacy Visit (Week 32) considering as observed for the analysis.

Secondary Estimand:

Summary measure (Population-level summary): LSmeans, together with the 95% CI and p-values based on the MMRM.

Intercurrent events and their corresponding strategies:

Intercurrent Events	Strategy for Addressing Intercurrent Events and Its Description
	Composite Strategy: A participant with this intercurrent event will be excluded from the analysis.

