5.4.1.3 Analysis Methods

Main Estimator (Analysis) for the Primary Estimand

A MMRM will be used to determine the change from baseline in Cardiovascular measurement at Week 16 or Week 32 in the open label phase to compare the participant groups of nicotine users vs non-nicotine users, will be analyzed using a MMRM based on observed case data. The models will include baseline CFR/GLS/cf-PWV measurement at Week 0, Baseline before first administration of guselkumab as a covariate, and Nicotine use, BMI, presence, or absence of PsA, age, gender, and visit.

The estimates for the primary estimand of the treatment effect of guselkumab will be provided by the difference of change from baseline at Week 32 in the LSmeans. The 95% CI for the differences in LSmeans and p-values will be calculated based on the MMRM. The within-subject covariance between visits will be estimated via an unstructured variance-covariance matrix. In case of convergence problems, alternative variance-covariance structures will be tried in the following order, with the first structure that converges being used in the analysis: heterogeneous Toeplitz, standard Toeplitz, and AR(1) with separate subject random effect.

5.5. Tertiary/Exploratory Endpoint(s) Analysis:

As the study was prematurely terminated all exploratory endpoints will be presented by listing only with change from baseline where applicable.

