5.7.8. Definition of Subgroups

The study will be conducted with a subgroup of nicotine users vs. non-nicotine users.

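### SAP 5.4.1 sorts participants by Week 0 CFR and reports change from that same value in a single arm, so category changes cannot be read as category-specific drug effects

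*SAP*

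**What the plan says.** The trial has one open-label arm. SAP 1.2 takes the Week 0 CFR as baseline, and SAP 5.1 defines change as the visit value minus that baseline. Entry requires CFR between 2 and 3.5 at both Screening Visit S2 and Week 0.

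SAP 5.4.1 lists, under its Key Confirmatory Secondary Endpoint(s) heading, CFR change at Weeks 16 and 32 "among participants with CFR in the ranges of 2 to >2.75 and ≤ 2.75 to 3.5 at baseline". SAP 1.1 and Appendix 2 give the cut as 2 to 2.74 and 2.75 to 3.5. Appendix 2 explains that the protocol's three ranges were reduced to two because few participants remained after early termination. The objective attached to this endpoint in 1.1 is the effect of guselkumab in the different CFR categories.

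No model is written for the categories. The MMRM in 5.4.1.3 includes the baseline value as a covariate but is described as a way "to compare the participant groups of nicotine users vs non-nicotine users, will be analyzed using a MMRM based on observed case data". It has no CFR-category term or interaction. SAP 5.7.8 names one subgroup factor: "The study will be conducted with a subgroup of nicotine users vs. non-nicotine users". The summary measure in 5.4.1.2 is "LSmeans, together with the 95% CI and p-values based on the MMRM", and 5.1 adds: "Nominal p-values will be presented".

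Two readings of CFR exist. Protocol 8.1 states: "To determine eligibility, the CFR results obtained at the study site will be used". Protocol 4.1 states: "All the CFR and GLS assessments in the study will be reviewed by a cardiology core lab for blinded analysis of endpoints", and SAP 5.3.1.1 agrees that "coronary parameters will be assessed by the cardiology core lab". The SAP does not say which reading sets the category.

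**The concern.** A low Week 0 reading is low partly because the person's CFR is low and partly because of error on that day. The same error then enters the change with a minus sign. Sorting by Week 0 CFR collects negative errors in the low category and positive errors in the high one, so later readings move the categories towards each other without any treatment. With no control arm, nothing in the category results separates this regression to the mean from a drug effect.

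At stake is a secondary result that could be read as a larger benefit at low baseline CFR, or as no benefit at high CFR, when noise produced it. The objective in 1.1 invites that reading.

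**Working it through.** **Plan figures.** The plan gives no figure for the category endpoint, so there is none to reproduce. From SAP 3 I take the planned mean change of 0.3 as the yardstick and the SD of 0.8. The planned 50 participants is not an input, and SAP 3 itself sets that calculation aside after termination.

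**Direction.** With no drug effect, write Week 0 = T + e0 and Week 32 = T + e32, where T is the stable true CFR. The change is e32 − e0. Since e32 is unrelated to the category,

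low change − high change = mean(e0 in high) − mean(e0 in low) > 0

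whenever there is any noise. Requiring CFR in range at both S2 and Week 0 does not remove this.

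**Size.** Simulation with T normal and independent noise at S2, Week 0 and Week 32; enrolment if S2 and Week 0 both lie in 2 to 3.5; split at Week 0 CFR 2.75; no drug effect; one reading used throughout. Assumed, not in the documents: between-person SD 0.5, source mean 2.75, and the noise SD. Reliability = 0.25/(0.25 + noise SD²). For example, 0.25/(0.25 + 0.40²) = 0.61. The largest noise SD, 0.57 = 0.8/√2, is an upper case that treats the whole planning SD as measurement noise in a change. The smallest is 0.5 × √(1/0.9 − 1) = 0.17.

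| Reliability | Noise SD | Low change | High change | False gap |
|---|---|---|---|---|
| 0.90 | 0.17 | +0.04 | −0.04 | 0.08 |
| 0.80 | 0.25 | +0.085 | −0.085 | 0.17 |
| 0.61 | 0.40 | +0.161 | −0.162 | 0.32 |
| 0.43 | 0.57 | +0.223 | −0.223 | 0.45 |

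Moving the source mean over 2.25 to 3.25 changes the gaps in the last three rows little (0.17 to 0.18, 0.32 to 0.33, 0.45). A second parameterisation, with total SD 0.5 to 0.7, source mean 2.5 to 3.0 and reliability 0.9 down to 0.3, gives gaps from 0.08 to 0.51, always in the same direction.

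**If someone compared the categories directly.** A raw two-sample t-test (Welch) of low versus high change would give nominal p<0.05 with no drug effect in about 14% to 40% of trials at an assumed 30 participants, and about 7% to 20% at 10 to 15. The final number is not in the documents.

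**Does the baseline covariate help?** Fitted separately in each category with Week 0 CFR as the covariate, a regression evaluated at the category's own mean baseline returns that category's raw mean change. The simulated values equal those in the table, so none of the gap is removed. With further categorical covariates at equal weights, the equality holds on average.

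**A no-treatment reference.** Week 0 minus S2 CFR, split by S2 category, shows the same phenomenon before any dose. At noise SD 0.25/0.40/0.57:

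| | Gap | 95% CI half-width |
|---|---|---|
| Endpoint artefact | 0.17/0.32/0.45 | – |
| Reference, 30 enrolled | 0.23/0.44/0.58 | 0.23/0.30/0.33 |
| Reference, all S2-eligible (33/37/42 people) | 0.13/0.26/0.39 | 0.24/0.35/0.44 |

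The enrolled-only reference overstates the artefact by about 30% (for example 0.58/0.45 = 1.29). The S2-eligible reference understates it (0.26/0.32 = 0.81).

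**The case against.** The strongest reply is that the SAP never plans the comparison that looks worst. It lists changes within each range and no low-versus-high contrast. That stands. A reader might infer that the SAP contains a specified test with a false-positive rate near 40%. The documents do not support this. The 14% to 40% belongs to a raw comparison that someone would have to add, at an assumed 30 participants. With covariates in separate category models, the rates at 30 participants and noise SD 0.25/0.40/0.57 fall to about 16%/21%/21%.

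A reader might also infer from 5.4.1.2 that p-values are planned for the categories. Its Variable paragraph names CFR at Week 16 and GLS and cfPWV at Weeks 16 and 32, not the CFR categories, so coverage is unclear. The heading in 5.4.1 adds little weight: the same list contains the adverse event rate, p-values are nominal, and the trial stopped early.

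The separate Data Presentation Specifications and the core-lab process document may settle the model and the reading, and neither is available here. The missing name of the reading is therefore housekeeping.

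What does not fall away is the bias within each category. It follows from the stated definitions of category and change, with or without a contrast. One could reply that a pooled model with continuous Week 0 CFR and a category term restores the 5% error rate. It does, but the term then measures only a departure from linearity at the cut. In simulation at 30 participants, a true effect of 0.5 below and 0.1 above a true CFR of 2.75 was detected in about 5% of trials, no more often than no effect.

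**Conclusion.** The point holds as one about interpretation and an unspecified analysis. Following SAP 5.4.1 as written yields category changes biased towards each other, and nothing else in the SAP corrects them or warns of it. The direction is certain given any measurement noise. The size is not: the gap is a minor 0.08 if CFR reliability is 0.9, about equal to the planned change of 0.3 near 0.6, and 0.45 in the upper case. All sizes rest on the assumed between-person SD, source mean and noise, and on one reading being used for entry, category and change.

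Opposite signs should not be expected as a signature, since a real effect common to both categories would shift both changes upward. The reversed inequality signs in the 5.4.1 ranges may come from text extraction and carry no weight. The change should be made, but it concerns one secondary endpoint and no confirmatory claim.

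**What to change.** 1. In SAP 5.4.1, label the CFR-category changes descriptive. State that neither a category's change nor a low-versus-high difference is to be read as a drug effect specific to that category.
2. Extend the S2 versus Week 0 comparison in 5.7.7. Report Week 0 minus S2 CFR by S2 category, in enrolled people and in all S2-eligible people with a Week 0 CFR, with 95% CIs, beside the category changes and using the same reading (site or core lab) as the endpoint. State its limits: it shows only the rough size of regression to the mean, it overstates the artefact by about 30% in enrolled people and understates it in all S2-eligible people, and its interval is about as wide as the estimate. It also spans only 2 to 4 weeks and may understate noise over 32.
3. Do not fit separate per-category models to support a between-category claim. Do not switch to S2 categories for the endpoint either: about a third of the artefact remains, with the opposite sign (−0.03/+0.03 to −0.07/+0.07).
4. As housekeeping, align the 5.4.1 ranges with 1.1 and Appendix 2, and name the reading that sets the category and the Week 0 baseline.

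The cost is SAP wording and a little more programming, since S2 and Week 0 CFR are already collected. The endpoint carries a weaker claim.
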